Appendix E – Body mass index, airflow Obstruction, Dyspnoea and Exercise index (BODE)

BODE Index for COPD

Scoring the BODE Index

	0	1	2	3
FEV ₁ % pred	≥65	50-64	36-49	≤35
6MWD (m)	≥350	250-349	150-249	≤149
MMRC	0-1	2	3	4
BMI (kg.m ⁻²)	>21	≤21		

Total BODE Index score = 0 to 10 units

(FEV₁% pred = predicted amount as a percentage of the forced expiratory lung volume in one second; 6MWD = six minute walking distance; MMRC = modified medical research council dyspnea scale; BMI = body mass Index)

Modified MRC Dyspnoea Scale	
0	Breathless only with strenuous exercise
1	Short of breath when hurrying on the level or walking up a slight hill
2	Slower than most people of the same age on the level because of breathlessness or have to stop for breath when walking at my own pace on the level
3	Stop for breath after walking about 100 meters or after a few minutes at my own pace on the level
4	Too breathless to leave the house or I am breathless when dressing

Appendix F – Algorithms/SAS Reference Codes

- **Calculation of adjusted means (least squares means):**

The approach described below will ensure that the least squares means calculated by SAS will be based on:

- coefficients for classification effects (i.e., the effects of categorical covariates) proportional to the margins observed in the group of patients analysed;
- effects of quantitative covariates set equal to their mean values in the group of patients analysed.

The analysis is based on the following steps:

1. generate a dataset by selecting:
 - in case of repeated post-randomisation measurements (e.g. FEV1 at each visit, analysed using a linear mixed model for repeated measures): all the post-randomisation records for patients with at least one available and valid post-randomisation measurement and no missing covariates;
 - in case of single post-randomisation measurement (e.g. number of COPD exacerbations during the Stabilisation Phase based on EXACT-PRO, analysed using a negative binomial model): all the patients with available and valid response and no missing covariates;
2. in case of repeated post-randomisation measurements, add to the dataset generated in step 1 the records for missing post-randomisation visits of the patients included in the dataset. In the added records the value of the response variable will be missing, but the full information on covariates has to be included;
3. use the dataset obtained as the input dataset for the MIXED or the GENMOD procedure, specifying the following options in the LSMEANS statement:
 - in case of repeated post-randomisation measurements: OM AT MEANS;
 - in case of single post-randomisation measurement: OM.

Example: analysis of change from baseline (Visit 1) at all visits (Visits 2 to 7) based on a mixed model for repeated measures including the effects of treatment, visit (categorical variable), treatment by visit interaction, baseline and another covariate.

Original dataset (X = available value; . = missing or invalid value):

Patient	Treatment	Covariate	Baseline	Visit	Change from baseline
1	A	X	X	1	.
1	A	X	X	2	.
1	A	X	X	3	X
1	A	X	X	4	X
1	A	X	X	5	X
1	A	X	X	6	X
1	A	X	X	7	.
2	B	X	X	1	.
2	B	X	X	2	.
2	B	X	X	3	X
3	C	X	X	1	.
3	C	X	X	2	.
3	C	X	X	3	X
3	C	X	X	4	.
3	C	X	X	5	X
3	C	X	X	6	.
3	C	X	X	7	X
4	B	X	X	1	.
4	B	X	X	2	.
5	A	.	X	1	.
5	A	.	X	2	.
5	A	.	X	3	X

Step 1 (visit 1 not selected since pre-treatment, patient 4 not selected due to missing post-randomisation measurements, patient 5 not selected due to missing covariate):

Patient	Treatment	Covariate	Baseline	Visit	Change from baseline
1	A	X	X	2	.
1	A	X	X	3	X
1	A	X	X	4	X
1	A	X	X	5	X
1	A	X	X	6	X
1	A	X	X	7	.
2	B	X	X	2	.
2	B	X	X	3	X
3	C	X	X	2	.
3	C	X	X	3	X
3	C	X	X	4	.
3	C	X	X	5	X
3	C	X	X	6	.
3	C	X	X	7	X

Step 2 (added records in *italic* and **bold**):

Patient	Treatment	Covariate	Baseline	Visit	Change from baseline
1	A	X	X	2	.
1	A	X	X	3	X
1	A	X	X	4	X
1	A	X	X	5	X
1	A	X	X	6	X
1	A	X	X	7	.
2	B	X	X	2	.
2	B	X	X	3	X
2	B	X	X	4	.
2	B	X	X	5	.
2	B	X	X	6	.
2	B	X	X	7	.
3	C	X	X	2	.
3	C	X	X	3	X
3	C	X	X	4	.
3	C	X	X	5	X
3	C	X	X	6	.
3	C	X	X	7	X

- **Tables that require Chi-Square test with continuity correction:**

```
PROC FREQ DATA = <dataset name>;
  TABLES <outcome variable>*<predictor variable> / CHISQ OUT=<output dataset
  name>
  OUTPUT OUT=stats;
RUN;
```

Notes:

- In case the assumption of Chi-square test is not met (e.g. expected cell frequencies < 5), a Fisher's exact test will be carried out. The SAS code is similar as above but with "FISHER" option in the "TABLES" statement above.

- **Tables that require One-way ANOVA test:**

```
PROC ANOVA DATA = <dataset name>;
  CLASS <predictor variable>;
  MODEL <outcome variable> = <predictor variable>;
RUN;
```

Notes:

- Should the normality assumptions for the outcome variable not be met (the skewness and kurtosis measurements will be considered as supportive indicators), the relationship between the outcome variable and the predictor variable will be tested using the non-parametric approach of Kruskal-Wallis test (or Wilcoxon Rank-Sum test for two groups). The SAS code used to implement this test will be:

```
PROC NPARIWAY DATA = <dataset name> WILCOXON;  
  CLASS <predictor variable>;  
  VAR <outcome variable>;  
RUN;
```

- **Tables that require Kaplan-Meier estimates and log-rank test:**

```
PROC LIFETEST data=dataset timelist=(0 t1 t2 t3 t4 t5 ... EoS) alpha=.05 outsurv=estim  
  reduceout;  
  TIME time*event(0);  
  STRATA trt;  
RUN;
```

Notes:

- Time represents the time to event or time to censoring;
- Event represents the censoring indicator (0 = censored);
- Trt represents the treatment group;
- EoS should be replaced by the last time to event >26 weeks (if any).

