- 2 Vital signs and laboratory assessments should where feasible be performed before salbutamol intake. Height is to be measured at Screening only. Vital signs include body temperature, RR, pulse rate, blood oxygen (measured using a pulse oximeter), systolic and diastolic blood pressure. If Screening and Day 1 are on the same day and there is no medical indication, then vital signs and physical examination noted for Visit 1 do not need to be repeated. If Visit 1 is performed over different days, vital signs and physical examination should be repeated on Day 1 prior to randomisation only if the subject's condition has deteriorated.
- 3 12-lead ECG will be performed after 10 minutes rest. If the Screening Visit and Day 1 are on the same day and there is no medical indication then the ECG noted for Visit 1 does not need to be repeated. If Visit 1 is performed over different days, the ECG should be repeated on Day 1 prior to randomisation.
- 4 For women of child-bearing potential only. Urine dipstick pregnancy tests carried out by site at Screening and at all indicated visits; serum pregnancy tests will be performed centrally at the Screening and last visit only. Urine pregnancy tests will be used for the purposes of inclusion into the study due to the acute nature of the study.
- 5 Prior to entry into the study (Visit 1), clinical laboratory tests will be performed at a local laboratory to confirm eligibility for randomisation. These tests will also be performed by the central laboratory. If Screening and Day 1 are on the same day and there is no medical indication, then the clinical laboratory tests noted for Visit 1 do not need to be repeated. If Visit 1 is performed over different days, the local laboratory should repeat clinical laboratory tests on Day 1 if the subject's condition has deteriorated.
- 6 All blood samples are to be collected at least 6 hours after SABA intake whenever possible (times of sample collection and SABA intake must be recorded), 8 hours fasting (where possible) and after ECG and vital signs (including RR). INR and prothrombin time not required during the Stabilisation phase.

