12.3 Laboratory Assessments

Haematology, blood chemistry, and urinalysis will be conducted at Screening, on Days 1, 3, 5, 7, 10 and 14, and at each visit in the Stabilisation phase.

Haematology, blood chemistry and pregnancy tests done at the Screening visit of the study should be sent to both the local laboratory and central laboratory for analysis. Haematology, blood chemistry and pregnancy done at all other visits of the study should be sent only to the central laboratory for analysis, with the exception of urine dipstick pregnancy test that should be done at the local laboratory.

Local laboratory normal ranges will be collected prior to first patient first visit (FPFV) at each site and provided to data management via the study team. Laboratory results collected from the local laboratory should be entered in the eCRF by the investigator.

The following parameters will be assessed:

- Haematology: red blood cell count, white blood cell count with differential counts and percentages, total haemoglobin, haematocrit, platelets count, INR and prothrombin time (INR and prothrombin time not required during the Stabilisation phase)
- Blood chemistry: creatinine, blood urea nitrogen [BUN], fasting serum glucose, AST, ALT, gamma-glutamyl transpeptidase, total bilirubin, albumin, chloride, calcium, phosphorous, uric acid, total protein, sodium and potassium
- Urinalysis (specific gravity, pH, protein, glucose, blood)
- Pregnancy test: serum β -HCG and urinary pregnancy test.

Blood collection and sample preparation will be performed according to procedures from the local and central laboratories.

If sputum or bronchoalveolar culture is collected for any medical reason (qualitative or quantitative culture), the result should be recorded in the eCRF and included in the safety analysis.

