13.5.2 Analysis of Primary Endpoint

FEV1 results (absolute values and changes from Baseline) will be summarised by treatment regimen and visit. Formal statistical analysis will be restricted to data collected up to and including Day 7.

The primary analysis of efficacy will be performed with the ITT population. Additionally for exploring the robustness of the intent-to-treat results, a supportive analysis using the PP population will be carried out.

Change of FEV1 from Baseline up to and including Day 7 will be assessed with a mixed-model repeated measures (MMRM) analysis, with treatment regimen as a factor and Baseline FEV1 as a covariate. The adjusted mean difference between regimens will be presented along with 95% confidence intervals for the Day 7 time-point.

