6.1 Intention-To-Treat population (ITT)

The ITT population includes all subjects who:

- Are randomised, and
- Receive at least one dose of study medication, and
- Provide a Baseline and at least one post-Baseline FEV1 value.

Patients will be included in the analysis per the treatment to which they were randomised.

Note: the 'Baseline' FEV1 value refers to the last non-missing FEV1 value assessed prior to the first dose of study medication.

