8.6.2.1 Primary analysis

The primary analysis of efficacy will be based on the ITT population and observed cases.

The primary analysis will compare each of the treatment regimens together using pairwise comparison tests based on a mixed model for repeated measurements (MMRM) using an unstructured covariance matrix and the Kenward-Roger adjustment for the denominator degrees of freedom. The model will use FEV1 absolute changes at Days 2, 3, 4, 5, 6 and 7, and will include treatment [REDACTED] severity of airflow limitation at baseline (post-bronchodilator FEV1 at baseline (pre-dose) <30% or ≥30% of predicted normal value), blood eosinophils (%) value at baseline (<2% or ≥2%), time from start of current COPD exacerbation to first IMP dosing (≤2 days, 3-4 days or ≥5 days), presence of cardiovascular comorbidities at screening (yes, no) and COPD exacerbation treatment at screening (systemic corticosteroids only, antibiotics only or both systemic corticosteroids and antibiotics) as fixed effects and baseline FEV1 value as covariate. In addition the baseline FEV1 value-by-visit and the treatment-by-visit interactions will be included in the model.

LSMEAN and standard error (SE) of each treatment regimen as well as the adjusted mean difference between treatment regimens and associated two-sided 95% CIs will be obtained from the MMRM model at Days 2, 3, 4, 5, 6 and 7. Each pairwise treatment regimen comparison will be tested at an alpha level of 5%. Difference will be considered and confirmed between pairwise treatments if the two-sided P-value for the test for difference is below 0.05. P-values of the effects will also be presented.

Hypotheses:

The 'superiority' null hypothesis will be:

$H_0: T2-T1 = 0$ (T2 is equivalent to T1) vs the alternative

$H_a: T2-T1 \neq 0$ (T2 is different to T1)

MMRM model and SAS code:

The SAS code used to implement linear mixed model for repeated measures for FEV1 and 95% CIs of differences between treatments will be similar to that shown below:

PROC MIXED data = dataset;

CLASS ID trt visit severity eosino time_symp cv_comorb COPD_trt;

*MODEL change = trt visit trt*visit severity eosino time_symp cv_comorb COPD_trt baseline*

*baseline*visit / ddfm=KenwardRoger;*

REPEATED visit / subject=ID type=UN;

*LSMEANS trt*visit / cl;*

LSMEANS trt / cl;

*LSMESTIMATE trt*visit*

'A vs B: Visit 2' 1 0 0 0 0 0 -1 0 0 0 0 0 0 0 0 0 0 0,

'A vs B: Visit 3' 0 1 0 0 0 0 0 -1 0 0 0 0 0 0 0 0 0 0,

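### Appendix F drops ITT patients with a missing eosinophil % or other added covariate from the primary FEV1 model

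*SAP*

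**What the plan says.** Protocol 13.5.2 specifies the primary MMRM "with treatment regimen as a factor and Baseline FEV1 as a covariate". SAP 8.6.2.1 keeps the ITT population and adds five categorical covariates: airflow severity, "blood eosinophils (%) value at baseline" split at 2%, time from symptom onset to first dose, cardiovascular comorbidity, and exacerbation treatment at screening.

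SAP 6.1 puts one data condition on ITT membership: "Provide a Baseline and at least one post-Baseline FEV1 value". It sets no condition on laboratory results or on any other covariate.

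SAP Appendix F, step 1, selects "all the post-randomisation records for patients with at least one available and valid post-randomisation measurement and no missing covariates" and gives FEV1 at each visit as its example. Step 3 then says to "use the dataset obtained as the input dataset for the MIXED or the GENMOD procedure". In the worked example, "patient 5 not selected due to missing covariate".

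On the source of the eosinophil value, Protocol 12.3 says that Screening haematology "should be sent to both the local laboratory and central laboratory for analysis" and that local results are entered in the eCRF. Footnote 5 to the schedule (Protocol 9.1.2) says that if Screening and Day 1 fall on the same day and there is no medical indication, "then the clinical laboratory tests noted for Visit 1 do not need to be repeated". SAP 8.1.7 takes the last assessment before first dose as the Visit 1 value for laboratory tests.

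**The concern.** Under the protocol's model, every ITT patient can be analysed, because ITT membership guarantees a Baseline FEV1. Under the SAP's model that is no longer so. A randomised, treated patient with complete FEV1 data can be left out because a pre-dose laboratory value or an onset date is missing.

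Two things are at stake. The analysis reported as ITT would be run on a subset with complete covariates, and FEV1 data already collected would be discarded. The second bullet of Appendix F step 1 applies the same condition to single-measurement analyses, and SAP 8.6.1 puts the same covariates in the other ANCOVA and repeated-measures models, so the effect extends beyond the primary endpoint.

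**Working it through.** **Does the rule govern the fit, or only the adjusted means?** The Appendix F text stands under adjusted means, but step 3 makes the reduced dataset the input to the procedure, so the whole model is fitted without these patients. Patient 5 in the worked example has a baseline and a Visit 3 change. That is enough FEV1 data for ITT, yet the patient is not selected.

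**Does anything bring them back?**
- SAP 7.2.1 covers missing values from subjects who dropped out, under missing at random. It gives no rule for a missing covariate, and none appears in 8.6.2.
- In SAP 8.6.2.3 the Day 7 ANCOVA lists the same covariates. The per-protocol MMRM and the V4.0/V5.0 MMRM name no different model. None restores the full ITT set.

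**Which covariates can be missing in an ITT patient?**
- Eosinophil %: only if there is no usable value at Screening or on Day 1 before dosing.
- Time from symptom onset: SAP 7.2.2.2 imputes a missing day as the 15th but leaves a missing month or year as missing.
- Comorbidity and exacerbation treatment: no rule is given.
- Airflow severity derives from baseline FEV1, which ITT requires, so it should rarely be missing.

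**Size.** Inputs from Protocol 13.1 and SAP 5: difference 100 mL, SD 230 mL, two-sided alpha 0.05, power 80%, 85 analysed per arm (255), about 5% dropout, about 270 randomised.

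The plan's own figure first. n per arm = 2 × (1.960 + 0.842)² × (230/100)² = 2 × 7.85 × 5.29 ≈ 83.0, which rounds up to 84. The t-based solution is 84.01, which rounds up to the stated 85. 255/0.95 = 268.4, so 269 against about 270. The plan's figures reproduce.

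Power = Φ(100 / (230 × √(2/n)) − 1.960). At n = 85: 230 × √(2/85) = 35.28; 100/35.28 = 2.834; 2.834 − 1.960 = 0.874; Φ = 80.9%.

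The documents give no missing rate, so a range is assumed. The last column starts from all 90 per arm having FEV1 data.

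| Assumed share missing | n per arm from 85 | Total | Power | Power from 90 per arm |
|---|---|---|---|---|
| 0% | 85.0 | 255 | 80.9% | 83.1% |
| 1% | 84.2 | 252 | 80.5% | 82.7% |
| 2% | 83.3 | 250 | 80.1% | 82.3% |
| 5% | 80.8 | 242 | 78.9% | 81.1% |
| 10% | 76.5 | 230 | 76.7% | 79.0% |

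The t-based values are about half a point lower (80.5% at 85 per arm; 78.4% after a 5% loss). These are two-sample approximations. The planning SD is not described as covariate-adjusted, so any precision gained from the added covariates is not counted.

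**The case against.** The strongest reply is that the trigger is rare and the consequence small. Local laboratory tests are required before entry to confirm eligibility, the haematology panel in Protocol 12.3 includes differential percentages, and the results go into the eCRF. SAP 8.6.1 and 8.1.7 take the last pre-dose value without limiting it to the central laboratory. On a plain reading, a local Screening eosinophil % already counts when the central one is absent. A reader might infer that one lost central sample removes a patient and that the plan forbids the second result. The documents do not support that: the order of precedence is unstated, but nothing rules the local value out. Nor do they show that same-day screening is the norm; they call it ideal.

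A reader might also infer bias. A pre-dose value cannot be missing because of treatment, so its absence gives no reason to expect a distorted comparison between arms. Setting the loss against the 15-patient difference between 270 and 255 would also mislead. That margin is for dropout, and the MMRM keeps a dropout who has any Day 2 to 7 value.

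The loss would be partly visible, since SAP 8.4.15 tabulates eosinophil class by regimen in ITT, and SAP 8.1.3 shows the number missing. Protocol 13.5.1 calls all analyses exploratory.

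All of this stands and limits the size of the point. It does not remove the mismatch: a patient with no usable value from either laboratory, or with no onset month, is in ITT and out of the primary model.

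**Conclusion.** The point holds as a mismatch between the declared population and the programmed one. The primary set will be smaller than ITT by the number of patients who lack any added covariate. At an assumed 1% to 5%, about 3 to 13 of 255 patients would leave (255 × 0.01 = 2.6; 255 × 0.05 = 12.8), and power would fall by 0.4 to 2.0 points, from 80.9% to between 80.5% and 78.9%. That range is an assumption; the true rate could be close to zero if local results are used. The harm is a modest, avoidable loss of precision and an inexact ITT label. No bias is shown. The change is worth making because it is cheap, not because the result is in danger.

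**What to change.** - In SAP 8.1.7, state that baseline eosinophil % is the last pre-dose central result or, if that is absent, the local result already in the eCRF.
- Code any categorical covariate still missing as a separate 'missing' level, collapsed if sparse, so that every ITT patient enters the primary FEV1 model.
- Change Appendix F step 1 so that its missing-covariate condition applies after this coding and only to continuous baseline values. Baseline FEV1 is guaranteed by ITT; the EXACT-PRO, CRQ and mMRC baselines in other models are not. Deleting the phrase alone would rescue nobody, because PROC MIXED drops records with a missing covariate by default.
- Report by arm how many patients needed the local fallback or the 'missing' level, and how many are still excluded from each model.

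The cost is SAP wording and programming, to be settled before unblinding. The small downside is that local and central results are mixed for a few patients and that a factor may gain a sparse extra level.

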13.4.2 Secondary Efficacy Endpoint(s)

Efficacy will be further assessed based on the following secondary endpoints:

1. Comparison of FEV1 on Days 3, 10, and 14
2. Normalisation evaluation of spirometry parameter (FEV1, FVC and FEV1/FVC) response over time (performed from Days 1 to 7, 10, 14, and at Weeks 8, 12 and 26) compared with the most recent test performed within the last 12 months outside and exacerbation (pre-study FEV1, FVC, and FEV1/FVC value)
3. Time taken to improvement of 100 mL in FEV1 compared to Baseline versus placebo
4. Comparison of AUC of FEV1 over time among groups
5. Change in RR over time (performed daily from Days 1 to 7, 10 and 14) among groups
6. Change in RR on Days 3, 7, 10 and 14 among groups
7. Time to improvement based on EXACT-PRO total score
8. Comparison of AUC of EXACT-PRO over time among groups
9. Number of COPD-related deaths during the study

10. Number of moderate/severe COPD-related exacerbations during the study
11. Time to next moderate/severe COPD exacerbation
12. Change from Baseline at each inter-visit period and over the entire period of the study in the average EXACT-PRO total score and domain scores
13. Number of times each subject required rescue therapy during the study
14. Time from hospitalisation until the subject is medically ready (COPD-related) for discharge
15. Nonlinear mixed effects PK/PD models evaluating the relationship between BCT197 exposure and efficacy/safety endpoints.

More details and the time points for collection are given in [Section 9.1.3](#) and in the Schedule of assessments ([Table 9-1](#)). A complete list of efficacy endpoints is given in [Section 11.2](#).

These secondary efficacy parameters will be assessed using the ITT population.

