The following figures will be produced for the EXACT-PRO rolling average score:

- Mean EXACT-PRO rolling average score over time by treatment regimen (Acute Exacerbation Phase and Stabilisation Phase separately).
- Mean EXACT-PRO rolling average score change from baseline over time by treatment regimen (Acute Exacerbation Phase and Stabilisation Phase separately).

The same analysis as above will be performed for each of the 3 EXACT-PRO subscores.

8.6.3.11 Number of COPD-related exacerbations during the study derived from 'Acute Exacerbation COPD' form of the eCRF

COPD-related exacerbations during the study derived from the 'Acute Exacerbation COPD' form of the eCRF will be considered for this analysis.

Only COPD exacerbations with symptoms start date \geq first study treatment intake on the form will be included in the analysis. The ‘date when symptoms started’ recorded on the form will be defined as the start date of the COPD exacerbation.

The number and the percentage of patients with COPD exacerbations, the number of COPD exacerbations and the total follow-up time in years will be summarised by treatment regimen.

The rate of COPD exacerbations per patient per year will be calculated for each treatment regimen using a weighted approach (which consists of pooling all patients of a treatment regimen and dividing the total number of COPD exacerbations by the total follow-up time).

The number and the percentage of patients with COPD exacerbations, the number of COPD exacerbations and the COPD exacerbation rate per patient per year as above will also be presented by treatment regimen for each of the following types of COPD exacerbation:

- Mild COPD exacerbations (intensity recorded as ‘Mild’ on the form)
- Moderate COPD exacerbations (intensity recorded as ‘Moderate’ on the form)
- Severe COPD exacerbations (intensity recorded as ‘Severe’ on the form)
- Moderate/Severe COPD exacerbations (intensity recorded as ‘Moderate’ or ‘Severe’ on the form)
- COPD exacerbations resulting in death (i.e. COPD-related deaths; serious criteria ‘Results in death’ ticked on the form)
- COPD exacerbations requiring hospitalisation (i.e. serious criteria ‘Requires in-patient hospitalisation or prolongs existing hospitalisation’ ticked on the form).

Additionally (and more generally), the number (%) of patients with COPD exacerbations and the number of COPD exacerbations will be presented by treatment regimen for each of the following category:

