- COPD exacerbations treated with systemic corticosteroids only (box ticked on the form)
- COPD exacerbations treated with antibiotics only (box ticked)
- COPD exacerbations treated with systemic corticosteroids and antibiotics (both boxes ticked)
- COPD exacerbations requiring invasive ventilation support (box ticked)
- COPD exacerbations requiring non-invasive ventilation support (box ticked)
- COPD exacerbations requiring Intensive Care Unit (ICU) admission (box ticked)
- COPD exacerbations with each of the following aetiologies: Infection, Environmental pollutants, Extrapulmonary co-morbidities, Concomitant pulmonary co-morbidities, Allergic, Other, Missing (if no aetiology was recorded). A multiple aetiology is possible: in this case the exacerbation will be counted in all the relevant categories.

The proportion of patients with COPD-related exacerbations during the study will be compared between treatment regimens using Pearson’s Chi-square test (or Fisher’s exact test as appropriate)

(two-sided test at 5% alpha level). This comparison will also be made for mild COPD-related exacerbations, for moderate COPD-related exacerbations, for severe COPD-related exacerbations and for moderate/severe COPD-related exacerbations separately.

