8.8 Other analysis

8.8.1 Efficacy analyses based on acute exacerbations of COPD adjudication

An independent, external IAC has been set-up to carry out responsibilities as detailed in the Independent Adjudication Committee Charter, Final Version 1.0, dated 07 February 2017.

Specific details regarding procedures for clinical adjudication of the components of the endpoint as well as the adjudication data collection/transfer process are fully described in the following documents:

- IAC Charter
- Systems Requirements Specifications, Final Version 2.0, dated 28 February 2017
- Data Delivery Specification, Final Version 1.0, dated 10 May 2017.

Once subjects have completed study treatment, the events to be adjudicated by the IAC are all new reports of acute exacerbation of COPD and events of hospitalisation due to new exacerbations of COPD (dataset AECOPD – AECOPD Adjudication Assessment). Each Adjudication case will be reviewed independently by each of the three adjudicators. If the adjudicators agree on all non-text fields the case will be complete and final. If they do not agree, they will meet and complete in Consensus.

The data derivations and statistical analyses to be performed based on acute exacerbations of COPD adjudication are described below:

- Number and percentage of patients with positively adjudicated moderate/severe COPD exacerbations will be provided by treatment regimen
- Number of positively adjudicated moderate/severe COPD exacerbations during the study will be provided by treatment regimen
- Rate of positively adjudicated moderate/severe COPD exacerbations per patient per year will be provided for each treatment regimen (same approach as for the non-adjudicated data)
- The proportion of patients with positively adjudicated moderate/severe COPD exacerbations during the study will be compared between treatment regimens using Pearson's Chi-square test (or Fisher's exact test as appropriate) (two-sided test at 5% alpha level)
- The time to next positively adjudicated moderate/severe COPD exacerbation will be analysed using the Kaplan-Meier method. Patients without a positively adjudicated moderate/severe COPD exacerbation or who are discontinued before having it will be

considered as “censored” patients. The same approach as for the non-adjudicated data will be used.

- Similar analyses as above will be performed for positively adjudicated moderate COPD exacerbations and for positively adjudicated severe COPD exacerbations separately.

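### The number of moderate/severe exacerbations is compared between arms only as any event versus none, so repeat events enter no between-arm comparison

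*SAP*

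**What the plan says.** Protocol 13.4.2 lists as secondary endpoint 10 "Number of moderate/severe COPD-related exacerbations during the study", and SAP 4.2 repeats it. Protocol 13.5.3 names no count model and leaves the detail to the SAP.

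SAP 8.6.3.11 takes events from the eCRF exacerbation form. It tabulates event counts by arm, and for the rate it says "The rate of COPD exacerbations per patient per year will be calculated for each treatment regimen using a weighted approach", meaning total events divided by total follow-up. The only between-arm test follows: "The proportion of patients with COPD-related exacerbations during the study will be compared between treatment regimens using" Pearson's chi-square or Fisher's exact test, repeated for moderate/severe events and the other severity classes.

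SAP 8.8.1 does the same for adjudicated events. It tests "The proportion of patients with positively adjudicated moderate/severe COPD exacerbations during the study will be compared between treatment regimens", while "Rate of positively adjudicated moderate/severe COPD exacerbations per patient per year will be provided for each treatment regimen" is descriptive.

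Time to next exacerbation is a separate endpoint (SAP 7.1.4.10, 8.6.3.13.1 and 8.8.1), analysed by Kaplan-Meier and log-rank with censoring at withdrawal or death.

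Appendix F, in explaining least squares means, gives as an example the count of EXACT-PRO-based exacerbations in the Stabilisation Phase, "analysed using a negative binomial model". Appendix C derives EXACT-PRO event frequency for that phase, but the body analyses only time to next EXACT-PRO event (8.6.3.13.2). Section 9 does not mention any of this.

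**The concern.** The endpoint asks how many exacerbations occurred, and the test asks whether there was at least one. A patient with three events counts the same as a patient with one. The log-rank test also stops at the first event, so no between-arm comparison uses a second or later exacerbation.

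Two things are at stake. The first is power on an endpoint for which 85 patients per arm is already few. The second is the estimate: the plan yields no rate ratio with a confidence interval, which is what a hypothesis-generating study would pass on to the design of the next trial.

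The proportion test also takes no account of time at risk. A patient who leaves early without an event is scored as event-free for the study.

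**Working it through.** **The plan's own figure.** SAP section 5 gives a difference of 100 mL, SD 230 mL, two-sided alpha 0.05 and power 80%. The normal approximation is n = 2 × (1.96 + 0.8416)² × (230/100)² = 83.04, so 84 per arm. With the noncentral t, 84 gives 79.99% and 85 gives 80.46%, so the stated 85 reproduces. 255/0.95 = 268.4, so 269, stated as about 270. No power is stated for exacerbations.

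**Inputs from the documents.** 85 per arm, 1:1:1 allocation, 26 weeks, two-sided 5% for each pairwise comparison without adjustment (SAP 8.6.1.1). The only background rate is 1 to 3 exacerbations per year (Protocol 7.1), a general COPD figure that the protocol says varies with severity. Over half a year, the expected control count is m1 = 0.5, 1.0 or 1.5.

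**Assumed, not in the documents.** Rate ratio (RR) 0.6 or 0.8, negative binomial dispersion k = 0.6, 1 or 2, equal follow-up, no covariates.

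**Formulas.**
- Probability of at least one event: P = 1 − (1 + k·m)^(−1/k).
- Proportion test: power = Φ[(|P1 − P2| − 1.96·SE0)/SE1], with SE0 = √[p̄(1 − p̄)·2/n] and SE1 = √{[P1(1 − P1) + P2(1 − P2)]/n}.
- Negative binomial Wald test: SE = √{[(1/m1 + k) + (1/m2 + k)]/n}, power = Φ(|ln RR|/SE − 1.96).

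**One case in full: 2 per year, RR 0.6, k = 1.** m1 = 1.0 and m2 = 0.6. P1 = 1 − 1/2 = 0.500 and P2 = 1 − 1/1.6 = 0.375. SE0 = √(0.4375 × 0.5625 × 2/85) = 0.0761 and SE1 = √(0.4844/85) = 0.0755. Proportion test: Φ[(0.125 − 0.1491)/0.0755] = Φ(−0.32) = 37%. Negative binomial: SE = √(4.667/85) = 0.2343, and Φ(0.5108/0.2343 − 1.96) = Φ(0.22) = 59%.

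**Power, proportion test / negative binomial (%):**

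| Events per year | k | RR 0.6 | RR 0.8 |
|---|---|---|---|
| 1 | 0.6 | 36 / 45 | 11 / 14 |
| 1 | 1 | 32 / 41 | 10 / 12 |
| 1 | 2 | 24 / 34 | 8 / 10 |
| 2 | 0.6 | 46 / 67 | 13 / 20 |
| 2 | 1 | 37 / 59 | 11 / 17 |
| 2 | 2 | 26 / 45 | 8 / 13 |
| 3 | 0.6 | 48 / 78 | 13 / 24 |
| 3 | 1 | 38 / 68 | 11 / 19 |
| 3 | 2 | 25 / 50 | 8 / 14 |

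The gain is 9 to 30 points at RR 0.6 and 2 to 11 points at RR 0.8.

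**Simulation check.** 2,000 trials per setting, 85 per arm, equal follow-up, with log-rank on first events added. At RR 0.6 and k = 1, power for chi-square, negative binomial and log-rank was 33.2, 41.1 and 33.4% at 1 per year, 38.5, 58.3 and 40.4% at 2 per year, and 37.8, 67.0 and 40.4% at 3 per year. With no true effect (k = 0.5, 1 and 2), rejection was 4.2-5.4% for chi-square, 4.6-6.2% for negative binomial and 4.2-5.3% for log-rank (Monte Carlo SE about 0.5 points). The slight liberality explains little of the gain.

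**Unequal follow-up.** Suppose patients who leave do so at times uniform over 26 weeks, unrelated to risk. At 3 per year and k = 0.6, the chance of an observed event is 0.657 for a completer and 0.420 on average for a patient who leaves. If one arm has 10 points more dropout, its observed proportion falls by 0.10 × (0.657 − 0.420) = 2.4 points. Over 1 to 3 per year and k = 0.6 to 2, the shift is 1.2 to 2.4 points.

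**The case against.** The strongest reply has four parts.

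- **Follow-up time is used elsewhere.** The log-rank analyses of moderate/severe events, eCRF and adjudicated, censor at withdrawal or death, and the descriptive rate divides by follow-up. This stands: the plan does not ignore time at risk altogether. It does not answer the point about repeat events, and log-rank power was close to chi-square in most settings.
- **The trial is exploratory.** Protocol 13.5.1 treats all analyses as exploratory, this is one of 15 secondary endpoints, and no power is claimed for it. This stands, and it limits the consequence.
- **The size depends on assumptions.** Rate ratio and dispersion are not in the documents. At a rate ratio of 0.8 both tests are weak (8-13% against 10-24%). This stands, so a range is given.
- **A count model needs definitions the plan lacks.** The model terms in SAP 8.6.1 include the baseline value of the analysed variable, which has no counterpart for an on-study count. Follow-up in SAP 7.1.2 runs from first dose, whereas the time-to-next clock starts when index symptoms stop. Both must be settled in the wording.

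A reader might infer that Appendix F shows a negative binomial rate analysis intended for endpoint 10 and then dropped. The text does not support that: the example concerns EXACT-PRO events in the Stabilisation Phase and states no offset. A reader might also infer that dropout materially biases the proportion test. At the assumed 5% dropout, with 255 of 270 expected to complete, the shift looks small. A gross imbalance would matter more: with an assumed 5% against 25% dropout, 3 events per year and no true effect, chi-square rejected 8.7% of the time and the model with offset 5.2%. If leaving depends on exacerbation risk, the offset alone does not remove the bias.

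**Conclusion.** The point holds. Endpoint 10 is defined as a count, and neither section that analyses it compares counts or rates between arms. Repeat events contribute only to descriptive tables.

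The negative binomial comparison had higher power in every setting tried. The direction is therefore firm, while the size rests on the assumed rate ratio and dispersion and on a general background rate. The model does not make the trial well powered for exacerbations: even at a rate ratio of 0.6, none of the tabulated settings reaches 80%. The firmer benefit is a rate ratio with its interval.

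The unused Appendix F example is a separate, smaller inconsistency about a different set of events. The FEV1 conclusion is not affected by either.

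**What to change.** In SAP 8.6.3.11 and 8.8.1, compare moderate/severe counts by negative binomial regression:

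- **Terms:** treatment and the fixed-effect factors of 8.6.1. Omit the baseline value of the variable, or replace it with the number of moderate or severe exacerbations in the 12 months before screening, which SAP 8.4.3 already summarises.
- **Offset:** log follow-up time as defined in 7.1.2. Section 8.6.3.11 counts events from first dose onward, so count and time share a start.
- **Report:** rate ratios against placebo with 95% CI. Keep the proportion with any event as supportive.
- **Fallback:** state in advance what is done if the model does not converge, which is possible with few events.

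Separately, add an analysis of the EXACT-PRO event count in the Stabilisation Phase to the body of the SAP, or delete the example from Appendix F.

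The cost is SAP wording and one extra model per endpoint. Counts, follow-up time and the factors are already collected or derived, so no new data are needed.
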